^e Contact 7 is the last Follow-up contact; it should occur approximately 10 days after Contact 6.

CGM Initiation in People with T2D

4. Schedule of Activities

	Baseline (10 days)	Intervention (~50 days including the 10-day post-intervention period)			Post-Intervention Assessment & Study Completion (10 days)		Follow-Up Assessment (10 days)	
Study Phase	Phase 1					Phase 2		
Contact	1	2	3	4	5	6	7	
Visit Type	Clinic (Day -11)	Clinic	Remote	N/A	Clinic	Clinic	N/A	
Study Day(s)¹	-11 to -1	0	14 (+7)	40 (+7)	50 (+7)	170 (+14)	180 (+7)	
Consent	X							
HbA1c	X				X	X		
Demographics	X							
Up to 10-Day Blinded G7 CGM Assessment	X					X		
Blinded G7 CGM Data Downloaded and Saved		X					X ⁶	
ASA24 Diet Recall	X	X ⁴		X ⁵	X	X ⁵	X	
DietID Diet Recall	X				X			
PROs: Diabetes Distress, Diet Adherence, Efficacy Surveys, and Diabetes Self Care	X				X	X		
PROs: Intervention Fidelity and Post-Intervention Surveys					X			
Diabetes Medication Assessment	X	X	X		X	X		

CGM Initiation in People with T2D

BP, Weight, Height ²	X				X	X	
Randomization ³	X ³						
Participant Receives Randomization Assignment		X ³					
CGM Initiation / Education (based on randomization arm)		X	X				
Continuous Real-time G7 CGM Use							
Real-time G7 CGM Data Downloaded and Saved			X		X		
Up to 10-Day Real-time G7 CGM Assessment Begins				X			
Adverse Events						X	

¹ If indicated, up to seven or 14 days can be added to or subtracted from the specified contact date to allow for scheduling flexibility; ² Height at baseline only; ³ Randomization occurs for scheduling purposes only; the randomization assignment is not shared with the participant during Contact 1 and will not be shared at Contact 2 until a minimum of 7 days of blinded G7 CGM data are confirmed; ⁴ This ASA24 is considered part of the baseline assessment and should occur before any of the Contact 2 activities ⁵ Two ASA24 assessments on non-consecutive days should be completed during the post-intervention and follow-up periods, one should occur on approximately Day 40 and Day 170 and one on approximately Day 50 and Day 180 ⁶ Participants may have the option to return receivers via postal mail; if this occurs, data download will be delayed
							

5. Phase 1 Background

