5. Change in patient-reported outcome survey scores from baseline to post-intervention 
 Diabetes Distress Scale-17 Score Diet Adherence Efficacy Survey Score 	Validated Diabetes Distress Scale Score, ⁴⁰ Diet adherence survey score, Efficacy survey scores; surveys administered via REDCap
6. Change in HbA1c from baseline to post-intervention	HbA1c assessed by either point-of-care fingerstick or venous draw
7. Change in body mass index (BMI) and body weight from baseline to post-intervention	Calibrated clinic scale and stadiometer; BMI calculated from measured weight and height
8. Describe fidelity to the intended intervention, including dose and content delivered, content enacted, and satisfaction	Data collection from study staff via paper documentation; and participant surveys administered via REDCap
9. Describe post-intervention patient-reported behavioral mechanisms	Participant surveys administered via REDCap

12. Phase 2 Study Outcome Measures

The Phase 2 follow-up assessment period is approximately 4 months and begins the day after Phase 1 is complete (approximately Day 51 to Day 180).

CGM-related outcome measures include approximately 10 days of CGM data collection during the baseline, post-intervention, and follow-up assessment periods. CGM data collection for the baseline and post-intervention are described under Phase 1 Study Outcomes Measures. CGM data at follow-up will be collected in the same way as baseline, which is up to 10 days of CGM data from a Dexcom G7 sensor paired with a physically blinded Dexcom receiver.

Primary Outcome

Outcome	Assessment Method
1. Change in CGM-derived TIR (% time with glucose 70-180 mg/dL) from post-intervention to follow-up for combined NFA and SDA arms	See CGM-related outcome measures described above

Exploratory Outcomes

Outcome	Assessment Method
1. Change in other CGM-derived core metrics from post-intervention to follow-up: 
 number of days CGM device is worn % time CGM sensor is active 	See CGM-related outcome measures described above

CGM Initiation in People with T2D

 • mean sensor glucose mg/dL • % coefficient of variation • glucose management indicator (GMI) • % time above >250 mg/dL • % time above >180 mg/dL • % time below <70 mg/dL • % time below <54 mg/dL 	

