Potentially eligible participants will have the option to complete online self-screeners (e.g. a brief questionnaire in REDCap) or undergo brief telephone screening. Any participants who meet initial screening criteria will be further screened by study staff for eligibility. Those who are eligible and express interest in study participation will receive additional study-related information, including a copy of the informed consent form (ICF). The ICF and other study-related materials may be shared by mail or electronically (e.g. email, EMR message, etc).

Up to 300 participants may be consented in order to obtain 120 participants who provide at least seven days of baseline and post-intervention CGM assessment data. It is assumed that some participants will consent, but they will not be eligible for participation based on the required HbA1c inclusion criteria; some participants will consent but may be withdrawn (e.g. due to inadequate days of CGM data at baseline); and that there may be approximately 10% attrition during the intervention period.

CGM Initiation in People with T2D

Consenting

All participants must meet all eligibility criteria and sign the IRB-approved ICF to participate in the study. During the consent process, study staff will explain the research to the participant and the participant will have ample opportunity to review the ICF and ask questions before deciding whether or not to participate in the study. The participant must sign the ICF before any study procedures are initiated.

Of note, during the screening and consenting process, Phase 1 of the study will be described to potential participants as a study evaluating the effect of two different approaches used for introducing and initiating CGM. Details of the NFA and the SDA will *not* be described to participants in order to reduce the potential for influence if details of both study arms are described to all participants before randomization assignments are given. Phase 2 of the study will be described as an opportunity to understand what happens when someone who has used CGM stops using it.

Once the ICF is signed, a copy of the ICF will be given to the participant and a participant ID number will be assigned.

Screen Failure

Participants who sign the consent to participate and who do not meet inclusion criteria in the baseline assessment period (e.g. HbA1c or tolerance to CGM) will be considered a screen failure.

CGM Device Use

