Once at least seven days of baseline G7 sensor data are confirmed, participants will receive their randomization assignment to either the NFA or the SDA arm.

Given that enrolling participants takes several months to complete, randomly permuted blocks of size two, four, and six will be used to ensure that participants are assigned to the NFA and SDA arms in approximately equal proportions over time. Randomization will be carried out within strata defined by participant's most recently available HbA1c $>8.5\%$ vs. $\leq 8.5\%$. The participant randomization schedule will be generated by the study statistician using a random number generator. Participants will remain in their assigned study arm throughout the intervention.

Blinding procedures are not described since blinding is not possible in a study comparing two different instructional approaches; the study staff and participants will know what type of instruction they give or receive. However, study participants will not know the details of the type of education provided to the other study arm (i.e. participants in the self-directed approach arm will not know the other arm is receiving a nutrition-focused approach and vice-versa).

Phase 1: Intervention

The intervention compares the effects of two different approaches used during CGM initiation, the NFA or SDA. For both arms, the intervention will include one in-person and one remote study appointment. All care and instruction will be provided by IDC research staff serving as interventionists. Intervention study staff will receive verbal training and written materials describing how to deliver the NFA and SDA; and checklists will be used to ensure consistent delivery among study staff and within each study arm.

On study Day 0, participants who have met all eligibility criteria and who have at least seven days of blinded CGM data will receive Dexcom G7 systems that will be paired with apps on their personal cell phone. Study staff will assist the participant in applying the G7 sensor, as needed. All participants will be instructed to wear and use the G7 and the associated phone apps continuously throughout the intervention, including changing out the sensors every 10 days or as needed. Intervention duration is expected to last approximately 50 days.

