Hypothesis (alternative): Participants randomized to a nutrition-focused approach (NFA) will show a higher total HEI score during the post-intervention than participants randomized to a self-directed approach (SDA).

Phase 2 Statistical Hypothesis

Primary Endpoint: Change in CGM-derived TIR (% time with glucose 70-180 mg/dL) from post-intervention to follow-up

Hypothesis (alternative): Participants will show a reduction in CGM-derived TIR from post-intervention to follow-up.

Sample Size Determination

Phase 1 of the study will enroll at least N=132 participants with the expectation for an analytic sample size of N=120. This sample size is based on the N needed to adequately power the primary hypothesis with a realistic and clinically meaningful effect size for % TIR. Specifically, existing research on CGM initiation in people with T2D shows mean TIR of 59% with SD of 25% after intervention.

An analytic sample size N=60 participants per arm has 80% power ($\alpha=.05$, two-sided) to detect an absolute differential change by study arm (i.e., more improvement in the NFA than SDA arm) of 12.9% from baseline to post-intervention (day 50). Justification to support a 12.9% difference in TIR requires converting A1c study data to TIR. The Mobile study showed a 0.4% decrease in A1c after CGM initiation in people with T2D using insulin; we expect a slightly smaller, 0.3%, improvement in our non-insulin using population. An eight-week nutrition intervention study showed a 1.2% decrease in A1c with the DASH diet; we expect a more conservative, 0.7%, improvement (in the NFA arm).

Using the A1c to TIR conversion (0.5% A1c reduction equals 10% TIR increase) suggests a 14% increase (difference) in TIR.

To account for approximately 10% attrition, the enrollment target will be set at N=66 per arm; total N=132.

CGM Initiation in People with T2D

The Phase 2 sample is dependent on the number of participants that complete Phase 1 and continue through the Phase 2 follow-up assessment period. It is expected that 90% of those completing Phase 1 (n=54/arm) will complete Phase 2 and have CGM data at follow-up. It is expected that 85% of those completing Phase 1 (n=51/arm) will complete Phase 2, have at least 7 days of CGM data at follow-up, refrain from CGM use during the follow-up period, and have no glucose-lowering medication changes during the follow-up period.

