With an expected sample size of n=54 per arm for the intention to treat (ITT) sample in Phase 2, the primary analysis has 80% power ($\alpha=.05$, two-sided) to detect an absolute change for pooled study arms of 0.27 standard deviation units of change in TIR from the end of the intervention to follow-up. For within-arm tests of change in this sample the primary analysis has 80% power ($\alpha=.05$, two-sided) to detect an absolute change within a study arm of 0.39 standard deviation units of change in TIR from the end of the intervention to follow-up.

Populations for Analysis

The analysis for Phase 1 will follow a modified intention to treat perspective, with an analysis of CGM metrics that includes only participants with at least seven days of CGM data at both baseline (approximately day -11 to -1) and post-intervention (approximately day 40 to 50).

The analysis for Phase 2 will follow a modified intention to treat perspective, with an analysis of CGM metrics that includes only participants with at least seven days of CGM data at both post-intervention and follow-up. This sample is utilized to assess the effect of discontinuation of CGM utilized in phase 1. A per-protocol (PP) analytic sample will consist of participants with at least seven days of CGM data at both post-intervention and follow-up who did not use CGM, and who did not require changes to glucose-lowering medications during the follow-up period. This PP sample is utilized to assess the effect of discontinuation on patients not utilizing CGM and having no medication adjustments during the follow-up period.

General Approach for Statistical Analyses in Phase 1

Baseline characteristics of study participants will be summarized with mean and standard deviation for interval data and proportions for categorical data. For analyses that do not concern total HEI or HEI component scores, the analytic models will utilize general and generalized linear mixed model repeated measures analysis to estimate differential change by study arm from baseline to post-intervention period. The link function and error distribution selected for each model will be based on the distribution of the endpoint. Each model will include fixed effects for study arm, time, their interaction, variables used in stratification, and a random intercept for patient. Each model will report the model-derived estimate (and 95% confidence interval) for the endpoint by study arm and by time period (baseline, day 50).

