The key analytic test for the primary endpoint will be based on planned contrasts reflecting the interaction of study arm and time period and will report and test model-derived estimates of differential change by study arm along with 95% confidence intervals. For the primary outcome, statistical comparisons will be made between and within arms and for study arm by time interaction with significance assessed at $p < 0.05$. A final Statistical Analysis Plan will specify further analytic detail and inclusion of any additional covariates.

For analyses of total HEI score and HEI component scores, mean scores will be computed separately at

CGM Initiation in People with T2D

each time point (pre-intervention, post-intervention) and for each study group. Confidence intervals for means will be based on a Monte Carlo approach implemented with code developed for the HEI-2015 utilizing a population ratio method appropriate for ASA24 data (e.g. HEI2015_ASA24-2016_MC_PopulationScore.sas). Note: if additional versions of HEI scoring, coding, and analysis become available, these may be used (e.g. HEI-2022).

Analysis of Primary Endpoint

The analysis of the primary endpoint tests whether patients randomized to a nutrition-focused approach (NFA) will have a larger increase in CGM-derived TIR from baseline to post-intervention than patients randomized to a self-directed approach (SDA). A general linear mixed model repeated measures analysis will estimate differential change by study arm from baseline to post-intervention period in TIR. The analytic model will include fixed effects for study arm, time, their interaction, variables used in stratification, and a random intercept for patient. A final Statistical Analysis Plan will specify any additional covariates to be included in the model.

Analysis of Secondary Endpoint

The analysis of the secondary endpoint tests whether patients randomized to a nutrition-focused approach (NFA) will have higher total HEI score at post-intervention than patients randomized to a self-directed approach (SDA). Mean total HEI scores and 95% confidence intervals computed for each study group will be compared to understand study group differences.

Safety Analysis

The trial does not have formal safety endpoints or formal rules or statistical guidance on stopping due to safety concerns. The review and reporting of AEs and SAEs is detailed in the Assessment of Safety and Safety Reporting sections.

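### The Phase 1 modified ITT set makes the primary TIR analysis a completer comparison, and no all-assigned or missing-data analysis of TIR is stated

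*Combined protocol and SAP*

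**What the plan says.** - **Analysis set.** Section 23, Populations for Analysis, describes Phase 1 as modified intention to treat, but the CGM analysis takes in "only participants with at least seven days of CGM data at both baseline (approximately day -11 to -1) and post-intervention".
- **Timing of randomisation.** Section 4, footnote 3, puts randomisation at Contact 1: "Randomization occurs for scheduling purposes only; the randomization assignment is not shared with the participant during Contact 1". Section 15, Randomization, adds: "Once at least seven days of baseline G7 sensor data are confirmed, participants will receive their randomization assignment". Staff know the arm.
- **Expected loss.** Section 15, Recruitment and Screening, expects that "some participants will consent but may be withdrawn (e.g. due to inadequate days of CGM data at baseline"), and separately about 10% attrition during the intervention. Section 23, Sample Size Determination, says: "To account for approximately 10% attrition, the enrollment target will be set at N=66 per arm; total N=132".
- **Short wear or early exit.** At Contact 5, a participant with fewer than seven days may extend wear or leave. Under section 17, investigators decide whether someone who terminates early or is withdrawn may complete final assessments.
- **Primary model.** A linear mixed model with arm, time, their interaction, the stratification variable and a random intercept, fitted to two time points.
- **Sensitivity analysis.** The only one named for Phase 1 is adjustment for prognostic factors, under exploratory endpoints. The per-protocol set belongs to Phase 2. For the rest, "A final Statistical Analysis Plan will specify further analytic detail and inclusion of any additional covariates"; missing data are not mentioned.

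**The concern.** The baseline half of the seven-day rule does little harm. It removes only people who were randomised but never told their arm. The post-intervention half is different: it selects on what happens after participants and staff know the arm, namely short wear without extension, exit or loss to follow-up.

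A mixed model can use a participant who has only a baseline value, and so adjust for loss explained by baseline TIR. The population rule removes those participants before the model is fitted. What remains is a complete-case comparison of change.

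If loss differs between arms in a way related to TIR, the primary estimate is biased, in a direction that cannot be known beforehand. The arms receive different instruction, and investigators who may know the arm decide who completes final assessments. These are possible routes to differential loss and not evidence of it. As written, no stated TIR analysis would reveal the problem. The exploratory outcome "Change in HbA1c from baseline to post-intervention" has no seven-day rule and gives a partial check, but it is a different outcome and has no post-intervention value for people who miss Contact 5.

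**Working it through.** **1. Planned figure.** Section 23 gives 60 analysed per arm, a difference of 12.9 points, SD 25 (stated for TIR after intervention) and two-sided alpha 0.05.
- SE = 25 × √(2/60) = 4.564.
- Two-sample t-test power = 0.800, so the stated 80% reproduces.
- Smallest significant estimate = 1.980 × 4.564 = 9.04 points.

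**2. Number excluded.** 132 − 120 = 12, or 6 of 66 per arm if split evenly. This treats all 132 as having been told their arm, which is an assumption.

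**3. Assumptions for the bias.** None of these is given in the documents:
- SD 25 at both times.
- Correlation ρ = 0.5 between baseline and post-intervention TIR (range 0.3–0.7). With ρ = 0.5 the SD of change is also 25.
- Loss q = 10% (range 5–10%).
- All lost participants come from one half of the distribution. This is strong selection, chosen for illustration.

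**4. Completer bias when loss is related to baseline TIR.** With h = √(2/π) = 0.798, losing a fraction q from one half shifts the completers' baseline mean by 25·h·q/(1−q) = 25 × 0.798 × 0.1/0.9 = 2.216 points. Their mean change shifts by (1−ρ) times that, in the opposite direction.

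| Case (ρ = 0.5) | Bias, points | Fraction of SE | Power for 12.9 | Type I error |
|---|---|---|---|---|
| Random, or alike in both arms | 0 | 0 | 80% | 5% |
| One arm, q = 10% | ±1.108 | 0.24 | 73% or 86% | 5.7% |
| Opposite in the two arms, q = 10% | ±2.216 | 0.49 | 64% or 91% | 7.7% |
| One arm, q = 5% | ±0.525 | 0.12 | 77% or 83% | 5.2% |
| Opposite, q = 5% | ±1.050 | 0.23 | 73% or 86% | 5.6% |

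Over q = 5–10% and ρ = 0.3–0.7, the one-arm bias is 0.3–1.6 points and the opposite-direction bias 0.6–3.1.

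**5. Milder selection in one arm (q = 10%, ρ = 0.5).** If a share f of the losses comes from one half, the bias is (2f − 1) × 1.108.
- f = 0.7: 0.44 points, power 77%, type I error 5.1%.
- f = 0.6: 0.22 points, power 79%, type I error 5.0%.

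**6. The same model fitted to all assigned participants.** Simulation with 1,000,000 per arm (Monte Carlo error about 0.04), q = 10%, ρ = 0.5:

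| Loss pattern | SD baseline/post | Completer | All-assigned |
|---|---|---|---|
| Low baseline, NFA only | 25/25 | −1.07 | 0.05 |
| Opposite selection | 25/25 | −2.21 | 0.01 |
| Low baseline, NFA only | 25/20 | −1.35 | −0.22 |
| Opposite selection | 25/20 | −2.67 | −0.41 |
| Low baseline, NFA only | 25/30 | −0.85 | 0.29 |
| Opposite selection | 25/30 | −1.76 | 0.51 |
| Low post given baseline, NFA only | 25/25 | 1.87 | 1.87 |

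The residual at unequal SDs arises because a random-intercept model assumes equal variances at the two times. In 4,000 simulated trials with 6 of 66 per arm baseline-only at random, the SE was 4.63 for completers and 4.58 for all assigned, so precision is essentially unchanged.

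**7. Loss that depends on the unobserved post value.** Bias = √(1−ρ²)·25·h·q/(1−q) = 0.866 × 2.216 = 1.92 points, the same in both analyses. The range is 0.8–2.1 over the q and ρ above with post SD 25. At q = 10% and ρ = 0.5 it is about 1.5 if the post SD is 20 and 2.3 if it is 30.

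**8. What a delta analysis would show.** With 6 of 66 missing in one arm, each 10 points of delta moves the estimate by 10 × 6/66 = 0.91. Holding SE at 4.564:
- An observed 12.9 loses significance at (12.9 − 9.04) × 66/6 ≈ 42 points.
- An observed 10.0 loses it at (10.0 − 9.04) × 66/6 ≈ 11 points.

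**The case against.** The strongest case against is that the effect is small. The 1.1-point figure needs every loss to come from one half of one arm. Milder selection gives 0.2–0.4 points and barely moves type I error. The 64% power and 7.7% error need complete selection in opposite directions, which nothing in the documents suggests. An observed 12.9 would survive a delta of about 42 points. All of this stands, and it is why the point is a safeguard and not a fatal flaw.

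Second, the all-assigned model corrects only loss explained by baseline TIR. It does nothing for outcome-dependent loss and adds no precision. That stands too, and is why a delta analysis belongs beside it.

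Third, CGM runs continuously from Day 0 and real-time data are saved at about Day 14 (Contact 3), so many later leavers would have some on-intervention TIR. This is fair. The figures in steps 6 and 7 treat only baseline as known and may overstate what cannot be recovered.

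Fourth, 12 of 132 is not firm. Section 15 counts a participant as enrolled once HbA1c qualifies, before baseline wear is confirmed, so some of the 132 may leave before learning their arm. However, the same section places the 10% attrition in the intervention period. Twelve remains an assumption.

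Fifth, ρ = 0.5 is not established by the planned power, because a post-only comparison with SD 25 also gives 80%. The range 0.3–0.7 is the safer statement.

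Finally, wear may be extended, the set is openly labelled modified, and a final SAP is promised. Extension reduces exclusions without ending them. The label discloses the restriction but does not test its effect. The promise of a SAP does not commit it to a missing-data analysis, so the claim is limited to what is stated here.

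**Conclusion.** The concern holds. Among participants told their arm, the Phase 1 TIR set excludes only on later events. The primary model therefore reduces to a completer comparison of change, and the protocol states no all-assigned or missing-data analysis of TIR. The plan's power figure is not in dispute.

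The bias is zero if loss is random or alike in both arms, and its direction otherwise cannot be predicted. The illustrative sizes rest on assumed values for the correlation, the rate and pattern of loss, and SD 25 at both times. They are upper-end illustrations and not forecasts. The point matters most for a result near the significance boundary of about 9 points. The change should be made because it is cheap and is credible only if stated before outcomes by arm are seen.

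**What to change.** State the following in the protocol or the promised SAP:

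1. **Primary analysis.** Fit the planned mixed model to every participant given an assignment at Contact 2, using all baseline TIR and any post-intervention TIR that meets a pre-stated minimum wear. Seven days can be kept as that minimum; participants below it contribute baseline only. Allow separate variances at the two times, which removes the residual bias seen when the SDs differ.
2. **Sensitivity analysis.** Keep the current seven-day set in this role.
3. **Missing not at random.** Add one simple pre-stated analysis, such as a delta shift by arm, because item 1 cannot correct loss that depends on unobserved TIR.
4. **Reporting.** Give, by arm and with reasons, the number randomised at Contact 1 but never told their arm, and the number excluded afterwards.

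The CGM data saved at Contact 3 could also inform the missing-data analysis; this is optional.

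The cost is SAP wording and a few model runs. No new data are needed: the Contact 2 column of the Schedule of Activities already has "Blinded G7 CGM Data Downloaded and Saved". The downsides are that delta values must be chosen in advance, and that item 1 helps only where loss depends on baseline TIR differently in the two arms.

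### The primary arm-by-time test is an unadjusted change-score comparison, and its 12.9-point power figure treats the post-intervention SD as the SD of change

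*Combined protocol and SAP*

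**What the plan says.** In Section 23, Analysis of Primary Endpoint, the model is given as: "The analytic model will include fixed effects for study arm, time, their interaction, variables used in stratification, and a random intercept for patient". The general approach for Phase 1 adds: "The key analytic test for the primary endpoint will be based on planned contrasts reflecting the interaction of study arm and time period". Estimates are reported at two times, baseline and day 50. Under Populations for Analysis, Phase 1 uses "an analysis of CGM metrics that includes only participants with at least seven days of CGM data at both baseline" and post-intervention. The stratification variable is HbA1c above 8.5% versus 8.5% or below (Section 15, Randomization).

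Under Sample Size Determination, the only SD offered comes from existing research that "shows mean TIR of 59% with SD of 25% after intervention". The text then claims 80% power with 60 per arm, two-sided 5%, to "detect an absolute differential change by study arm (i.e., more improvement in the NFA than SDA arm) of 12.9% from baseline to post-intervention". The Phase 2 power statement uses a different unit: "0.27 standard deviation units of change in TIR from the end of the intervention to follow-up".

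On further adjustment, the primary endpoint section says: "A final Statistical Analysis Plan will specify any additional covariates to be included in the model".

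**The concern.** There are two linked problems.

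**Model form.** Baseline TIR enters as an outcome row, not as a covariate. With complete pairs at two times, anything constant within a patient cancels from the interaction contrast. The analysis looks adjusted for the stratification factor, but its primary test is not. It also forces the regression of post-intervention TIR on baseline TIR to have slope 1, whereas ANCOVA would estimate that slope.

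**Power.** The tested quantity is a change, but the SD quoted is for a single time point. The 80% claim therefore belongs to the planned test only under a condition that the plan does not state.

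Under randomisation the contrast is unbiased. What is at stake is precision, and whether the stated power describes the test that will be run.

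**Working it through.** **Inputs from the documents:** 60 per arm, two-sided 5%, 80% power, difference 12.9, post-intervention SD 25. **Not in the documents:** the baseline SD (s0) and the baseline to post-intervention correlation (rho). Both are assumed over a range below.

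**1. The plan's figure.** A two-sample noncentral t calculation with SD 25 and 60 per arm gives a detectable difference of 12.89 and power of 80.0% at 12.9. The largest SD of the tested quantity that still gives 80% at 12.9 is 25.01. So 25 was used as the SD of change.

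**2. The contrast.** For each patient, post minus baseline removes the random intercept, the stratum and any other term constant over time. With complete pairs, what remains is the comparison of mean change between arms. This was checked on simulated complete pairs (60 per arm, both SDs 25 within stratum):

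| rho | Mixed model with stratum: estimate (SE) | OLS of change on arm: estimate (SE) | ANCOVA SE | ANCOVA slope |
|---|---|---|---|---|
| 0.3 | 8.5286 (5.155) | 8.5286 (5.155) | 4.258 | 0.32 |
| 0.5 | 4.6050 (4.867) | 4.6050 (4.867) | 4.019 | 0.41 |
| 0.7 | 10.1822 (3.650) | 10.1822 (3.650) | 3.318 | 0.64 |

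Dropping the stratum left every estimate unchanged. In a further simulated trial, adding age, or baseline TIR itself, only as a main effect also left the estimate unchanged. The match in SEs assumes a non-negative patient variance.

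**3. When SD 25 is adequate.**

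SD of change = sqrt(s0² + 25² − 2·rho·s0·25).

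This is at most 25 when s0² ≤ 50·rho·s0, that is, when rho ≥ s0/50. The correlation needed is 0.30, 0.40, 0.50 and 0.60 for s0 = 15, 20, 25 and 30.

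**4. Planned against adjusted.** The adjusted residual SD is 25·sqrt(1 − rho²). At rho 0.5 it is 25 × 0.866 = 21.65, whatever s0 is. The entries below are in the order rho 0.3 / 0.5 / 0.7.

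| s0 | Power at 12.9, planned (%) | Power at 12.9, adjusted (%) | Variance ratio, adjusted/planned | Detectable difference, planned |
|---|---|---|---|---|
| 15 | 80 / 90 / 97 | 84 / 90 / 98 | 0.91 / 0.99 / 0.98 | 12.9 / 11.2 / 9.3 |
| 20 | 74 / 86 / 97 | 84 / 90 / 98 | 0.78 / 0.89 / 0.98 | 13.9 / 11.8 / 9.3 |
| 25 | 66 / 80 / 95 | 84 / 90 / 98 | 0.65 / 0.75 / 0.85 | 15.3 / 12.9 / 10.0 |
| 30 | 57 / 71 / 90 | 84 / 90 / 98 | 0.53 / 0.60 / 0.67 | 16.9 / 14.4 / 11.2 |

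The adjusted detectable difference is 12.3 / 11.2 / 9.2 in every row. The true slope is 25·rho/s0. At s0 = 15 and rho = 0.6 it equals 1, the variance ratio is 1.00 and nothing is gained.

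**5. Simulation (3,000 trials per cell).** Power for the change score against ANCOVA with stratum was 0.739 against 0.815 (s0 20, rho 0.3), 0.649 against 0.818 (s0 25, rho 0.3) and 0.801 against 0.890 (s0 25, rho 0.5). In the three null settings tried, rejection rates were between 0.046 and 0.054 for both tests.

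**6. Phase 2 for comparison.** One-sample t on change gives 0.272 SD for n = 108, which matches the stated 0.27. Phase 2 power is therefore in the correct unit.

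**The case against.** - **The 12.9 is not shown to be wrong.** Equal SDs of 25 with correlation 0.5 give an SD of change of exactly 25. This stands: the figure is unsupported, and power could be higher or lower than stated.
- **The worst rows may be unrealistic.** Entry HbA1c spans 7.0% to 10.0%. The plan's own conversion (0.5% HbA1c equals 10 TIR points) turns that into 60 TIR points. A uniform spread has SD 60/sqrt(12) = 17.3, and an assumed 10 points of scatter makes it sqrt(300 + 100) = 20. With s0 of 15 to 20 and rho of 0.5 to 0.7, planned power is 86% to 97% and the variance ratio is 0.89 to 0.99. If both SDs were 20, planned power would be 84% even at rho 0.3. This is fair, but only indicative. With post SD 25, s0 = 20 and rho = 0.3, planned power is still 74%.
- **Adjusted power is slightly optimistic.** The formula treats the slope as known. Allowing for estimation of slope and stratum gives 79.4% at rho 0 and 83.0% at rho 0.3. This stands, and the difference is small.
- **A final SAP is promised.** It could change the model form under further analytic detail, but the promise of covariates does not do so. A covariate entered only as a main effect leaves the estimate where it was.
- **It is a non-pivotal pilot.** Even so, the sample size text says N was chosen to power the primary hypothesis and claims 80%.

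**Conclusion.** The concern holds on both parts. That the planned contrast is an unadjusted change-score comparison follows from the stated model and analysis set and needs no outside assumption. The 80% power at 12.9 belongs to that contrast only if rho ≥ s0/50, and the plan states neither quantity.

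The size of the loss depends on assumed values. With post SD 25, it runs from nothing (true slope near 1) to 66% against 84% power at s0 25 and rho 0.3, and further if baseline spread is larger. At s0 25 and rho 0.5, adjustment cuts the variance by 25%, and 46 per arm would do the work of 60. With adjustment, the plan's 12.9 holds to within about half a percentage point of power at any non-negative correlation and any baseline SD, provided the post-intervention SD is 25.

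This is lost efficiency and an incomplete power justification. It is not bias. It should be changed, but it does not invalidate the trial.

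**What to change.** In the final SAP, name one baseline-adjusted test as primary. Either of these would serve:

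- ANCOVA of post-intervention TIR on arm, baseline TIR and HbA1c stratum; or
- a longitudinal model with a common baseline mean across arms, stratum-by-time and an unstructured 2×2 covariance.

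The planned mixed model can stay for the by-arm, by-time and within-arm summaries. If ANCOVA is chosen, note that the adjusted arm difference will generally not equal the difference between those within-arm changes. The longitudinal form avoids this if the summaries are taken from the same model.

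In the sample size text, say that 25 is the post-intervention SD and that power refers to the baseline-adjusted test. If the change-score contrast is kept, give the SD of change, or the baseline SD and correlation, behind 12.9.

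**Cost:** one model statement and one sentence before the final SAP is signed. The text naming the interaction contrast as the key test needs editing, as do the sections that borrow the primary framework for exploratory endpoints and Phase 2. No patients or data are added, because baseline TIR is held for everyone analysed. The estimand is unchanged. The pooled Phase 2 contrast is a within-patient change and can stay as it is.
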